The SMS conduct interim-monitoring visits (IMV) to insure compliance and safety. The first IMV will be scheduled following the enrollment of the first 1-2 subjects. Subsequent IMVs will be scheduled to occur approximately quarterly. The schedule may vary based on study enrollment rate. Unscheduled visits may be conducted based on reports or evidence of potential noncompliance, significant increases in subject enrollment rates, or changes in protocol/personnel and training activities. SMS service agreement is attached to the ARROW application.

ASSESSMENT OF SAFETY

Adverse Event (AE)

Adverse event (AE) means any untoward medical occurrence associated with the use of an intervention in humans, whether or not considered intervention-related.

This study will utilize the Common Terminology Criteria for Adverse Events (CTCAE) v5.0 for adverse event monitoring and reporting. The CTCAE v5.0 is the default version available in the ICTR OnCore system and applied by default in the electronic adverse event log.

This information can also be downloaded from the CTEP home page (http://ctep.info.nih.gov/CTC4/ctc_ind_term.htm).

The severity of the event will be graded using the CTCAE. In addition, for comparison to the CTCAE, adverse events will be tabulated using a 3-level schema as defined below:

Mild: event may be noticeable to patient; does not influence daily activities; usually does not require intervention.

Moderate: event may be of sufficient severity to make patient uncomfortable; performance of daily activities may be influenced; intervention may be needed.

Severe: event may cause severe discomfort; usually interferes with daily activities; patient may not be able to continue in the study; treatment or other intervention usually needed.

Note the distinction between the severity and the seriousness of an AE. A severe event is not necessarily an SAE. For example, a headache may be severe (interferes significantly with patient's usual function) but would not be classified as serious unless it met one of the criteria for SAEs.

Next, it will be determined by the study physician(s) whether the event is expected or unexpected and if the AE is related to the intervention or procedure or administer the intervention. With this information, it will be determined whether an AE should be reported as an expedited report in addition to submission via routine clinical data.

Expedited AE reporting may require e-mail notification, phone, or fax submission of a written report as directed below. All expedited AE reports will be submitted to the FDA (if applicable) and the IRB of record, the UW Health Sciences Institutional Review Board (HSIRB) in the case of this study.

Serious Adverse Event

A serious adverse event (SAE) is an AE occurring during any phase of the study (i.e., screening, admission, treatment, or follow-up) that fulfills one or more of the following criteria:

- Results in death
- Is immediately life-threatening
- Requires in-patient hospitalization or prolongation of existing hospitalization (more than 24 hours)
- Results in persistent or significant disability or incapacity
- Is a congenital abnormality or birth defect
- Is an important medical event that may jeopardize the subject or may require medical intervention to prevent one of the outcomes listed above.

Unanticipated Problem (UP) Definition

The Office for Human Research Protections (OHRP) considers unanticipated problems involving risks to participants or others to include, in general, any incident, experience, or outcome that meets all of the following criteria:

- The incidence, experience, or outcome is unexpected given the research procedures described in protocol-related documents (e.g., the study protocol, the consent documents, the Investigator's Drug Brochure) and the characteristics of the subject population being studied. An event may be considered unexpected if it exceeds the

nature, severity, or frequency described in the study-related documents, Investigator's Drug Brochure, product labeling, or package insert.

- The incidence, experience, or outcome is related or probably related to participation in the research study. Probably related means the incidence, experience, or outcome is more likely than not to be caused by the research study procedures.
- The occurrence of the incidence, experience, or outcome suggests that the research places participants or others at a greater risk of harm (physical, psychological, economic, or social) than was previously known or recognized.

Assessment of Attribution

The PI or sub-investigator study physicians will assess adverse events to determine the attribution or relatedness to the study procedures and/or intervention. When assessing whether an adverse event is related to a medical treatment or procedure, the following attribution categories are utilized:

Definitely Related: An AE categorized as Definite is clearly related to the intervention. If the timing of the AE is definitely consistent with the exposure to the study intervention and it is most likely that the AE was caused by the study intervention such as because a high occurrence of the AE was expected based on the study intervention materials? In this case, the PI may categorize the AE as definitely related.

Probably Related: An AE that is likely related to the use of the drug. A Probable AE is likely related to the intervention. If the timing of the AE is consistent with the exposure to the study intervention and it is more likely that the AE was caused by the study intervention than not, the PI may categorize the AE as Probable.

Possibly Related: An AE that may be related to the use of the drug. If the timing of the AE is reasonably consistent with the exposure to the study intervention, and there is another cause of the AE that could be equally likely, the PI may categorize the AE as Possible.

Unlikely Related: An Unlikely AE is one that is doubtfully related to the intervention. The coincidence of the AE with the exposure of the investigational product or intervention should be assessed. An AE that continued while the intervention was interrupted or stopped, or if the AE resolved while the intervention continued, may be categorized as Unlikely. If there is another more likely cause of the AE, the PI may determine that the AE was unlikely related to the study intervention.

Not Related/Unrelated: An Unrelated AE is one that is clearly NOT related to the intervention. An AE may be considered Unrelated if the subject did not receive the study intervention or if there is another obvious cause of the AE (for example, a car accident or other disease/condition).

Adverse Events of Special Interest

Adverse events pertaining to the subject (mother) or neonate child occurring after the signing of consent until 6 weeks post-delivery, will be collected. Conditions that are

routinely encountered by obstetricians or pediatricians, such as C-section or infant jaundice, will be recorded on the adverse event log, but will not be reported (i.e. entered into OnCore) per clinical investigator's judgement. All adverse events meeting the HS-IRB reportable event requirements will be entered into OnCore, regardless of being considered a routine condition.

Adverse events that are expected in pregnancy and assessed as not related/unrelated to the protocol will not be reported to the ICTR DMC and entered into OnCore. These events include but are not limited to nausea and vomiting, dizziness, abdominal discomfort, back pain, vaginal discharge, and Braxton Hicks contractions.

Given the exclusion criteria and MRI screening, we do not anticipate any major events related to the MRI procedure. However, it is possible that patients report claustrophobia or anxiety in the large bore MRI machines. This may potentially require that we reduce the BMI cutoff from 39.9 Kg/m² to a lower value for the purpose of our study examination. The adverse response and claustrophobia concerns, even in a wide bore MRI research equipment, is one of the reasons we are choosing the BMI range of 18.5-39.9 Kg/m² for our study purposes.

Any planned hospitalizations for the delivery will not be reported as an SAE, but if any AE occurs during delivery or if the hospitalization is lengthened due to safety concerns this will be reported.

Genetic conditions, birth defects, or cardiac defects not recorded or suspected prior to consent will be documented as adverse events.

Any event may be documented and followed for up to 1 year post-delivery upon investigator's discretion.

Serious Adverse Event Reporting Requirements

Adverse Events that are:	Notify HS IRB	Notify DMC	Notify FDA** (events related to Ferumoxytol-MRI only)
Serious Suspected/Related* Unexpected	Within 14 business days	Within 14 business days	Notify FDA and all participating institutions as soon as possible, but no later than 15 calendar days after learning of the event
Serious Life threatening or Fatal Suspected/Related* Unexpected	Within 1 business day (24 hours) of learning of the event.	Within 1 business day (24 hours) of learning of the event.	Within 7 calendar days of learning of the event

* The UW-Madison HSIRB requires immediate reporting of serious adverse events that are probably or definitely related, whereas the FDA requires reporting of these events that are possibly, probably or definitely related. Therefore if an event is reported to the HSIRB, the event will also be reported to the FDA.

Reporting requirements to the ICTR Data Monitoring Committee

All recorded AEs will also be available to the ICTR DMC by completing the AE/SAE forms in OnCore. The reporting requirements are consistent with those of the HS IRB, as well as the same timeframe. Once entered into OnCore, an automatic notification of an SAE will be sent to the ICTR DMC as an automated notification.

Study Stopping Guidelines

The study will be stopped or significantly changed if at least one of the following occurs:

- More than 10% of subjects experience severe claustrophobia or severe anxiety related to the MRI procedure
- For subjects receiving ferumoxytol, the study will be stopped or significantly changed if 2 subjects have an anaphylactic reaction

Subject Stopping Guidelines

If the subject experiences any adverse events or any issues arise that may affect the subject's safety, the subject will be withdrawn from the study.

The Principal Investigator (PI) may discontinue or withdraw a subject from the study for the following reasons at his/her discretion:

- If any clinical adverse event (AE), laboratory abnormality, or other medical condition or situation occurs such that continued participation in the study would not be in the best interest of the subject
- There is evidence of progressive disease or unacceptable toxicity

BIBLIOGRAPHY

4. Catalano P, deMouzon SH. Maternal obesity and metabolic risk to the offspring: why lifestyle interventions may have not achieved the desired outcomes. *Int J Obes (Lond)*. 2015;39(4):642-9. doi: 10.1038/ijo.2015.15. PubMed PMID: 25777180.

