The patient's clinical provider will be informed that the patient is participating in the FGR study and that, if any unknown conditions or illnesses are identified during the course of prenatal care, we would appreciate knowing from them with patient's consent. We also set up a mechanism in the obstetrics triage unit in the UnityPoint Health-Meriter inpatient facility for all pregnant women admissions to include a specific alert for the nursing staff that the patient is a study participant and that patients should be informed, and, with the patient's permission, study coordinator can be notified for any new conditions and/or illnesses.

SUBJECT POPULATION AND ELIGIBILITY CRITERIA

Sample Size

The total sample size is 20.

Inclusion Criteria

1. Pregravid BMI 18.5-39.9 Kg/m²
2. Women with singleton pregnancies
3. Ultrasound confirmed pregnancy dating prior to 14 weeks gestation
4. Gestational age of 27 0/7 - 32 6/7 weeks at FGR diagnosis based on standard clinical criteria.
 - a. Estimated Fetal Weight: less than 10 percentile OR
 - b. abdominal circumference less than 10th percentile

Exclusion Criteria

1. Diagnosis of preeclampsia at FGR diagnosis
2. Gestational Diabetes Mellitus or type I/II Diabetes Mellitus
3. Known fetal chromosome abnormality, structural malformation or syndromes in current pregnancy
4. Known fetal viral infection syndrome
5. Alcohol/drug/tobacco use in current pregnancy
6. History of sickle cell anemia, sickle cell trait or other inherited anemia with risk of iron overload
7. Contraindications to MRI (such as claustrophobia, metallic implant, etc.) based on MRI Screening

8. Participation in other interventional clinical trials, including those with other investigational agents not included in this trial, within 30 days of the start of this trial and throughout the duration of this trial
9. Any physical or psychological symptom, based on the clinical judgment of the study physician that would make a participant unsuitable for the study.

Final subject eligibility will be determined by the Principal Investigator or Sub-Investigator delegated the corresponding task.

SUBJECT IDENTIFICATION AND RECRUITMENT

Identification in clinical practice: Investigators own practice

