We are not proposing a new route of administration for this approved drug. However, we are proposing to use this drug in pregnant women. Pregnant women are at risk for developing clinical complications of pregnancy including preeclampsia and fetal growth restriction. These complications are unique to pregnant women. There have been limited investigations on pregnant women to advance the science leading to development of technologies that may help identify women who may develop these complications, before they clinically manifest these complications.

Once there are clinical manifestations of these complications, there is nothing that can be done to prevent these complications and currently options for treatment are non-existent except temporization to provide limited benefit to developing baby at significant risks to the mother by postponing delivery. Hence, it is essential and critical that we conduct such studies in pregnant women to advance this science and develop advanced tests of placenta function with high degree of precision to help mothers and their babies in the future.

Limited available data with ferumoxytol use in pregnant women are insufficient to inform a drug associated risk of adverse developmental outcomes. There are risks to the mother and fetus associated with untreated IDA in pregnancy, which far exceeds the risks and benefits of Ferumoxytol infusion during pregnancy. In animal studies, administration of ferumoxytol to pregnant rabbits during organogenesis caused adverse developmental outcomes including fetal malformations and decreased fetal weights at maternally toxic doses of 6 times the estimated human daily dose.

Impact on the Fetus

Regarding the impact of the agent on the fetus, the physiology of colloid iron supports the statement that ferumoxytol does not cross the placenta and enter the fetal circulation. All iron is absorbed in the macrophages in the maternal immune system. Ferumoxytol does not cross the placenta as all iron is cleared by the mother. It was determined that this iron does not go into the fetal circulation, as it is a colloidal superparamagnetic iron carbohydrate complex that is trapped in the maternal immune system.

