Critical analysis of literature suggests that anaphylaxis may occur in 0.02 % of subjects receiving ferumoxytol, making it one of the safest intravenous iron preparation. Furthermore, the data on SAEs derived from Adverse Event Reporting System have inherent limitations of limited information on safety precautions taken prior to iron infusion and treatments rendered for suspected adverse events, since some of the treatments used for drug reactions to intravenous iron themselves have inherent risks of causing serious adverse events compounding the interpretation of these data.

Other common adverse reactions reported in Ferumoxytol-treated patients include diarrhea (4.0%), constipation (2.1%) and hypertension (1.0%).

Toxicological data in animals or prior studies in humans with ferumoxytol does not suggest additional risks of particular severity or seriousness over and above what is

described above. This is so because we plan to use substantially lower dose during gestational window well beyond the period of organogenesis.

If there is an unforeseen adverse reaction, we would use the usual and customary treatment for iron infusion-associated allergic reactions, which would be no different from response to any other allergic reaction case at the obstetric triage unit. In order to facilitate and create the utmost safety, we would pre-notify the obstetric anesthesiologist on the unit in advance of the scheduled procedure. After the patient completes intravenous iron infusion and has been monitored for at least a total of an hour and has not experienced any adverse side effects, the patient will be advised to present herself for the ferumoxytol-MRI. The coordination for this will be provided by the study coordinator assigned to the study.

The vast majority of serious allergic reactions occur within short time (10 minutes) of starting the infusion. No reactions have been reported after 30 minutes of infusion. We have arbitrarily extended observation period to one hour and no one is expected to develop allergic reactions after that time.

Patients have hemogram done routinely for clinical care at 28 weeks. We will perform a panel of iron study (serum iron and transferrin levels) two-three weeks after the day of infusion. TIBC is not useful in settings of patients having received iron infusion, hence is not included in the panel.

Supporting Documentation for Safety of Ferumoxytol use in Pregnant Women

Ferumoxytol - Pregnancy reports in AMAG safety database

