Specific Aim 1: MRI Flow

- 2D Phase Contrast MRI (Flow Imaging) = FDA approved, clinical sequence

Specific Aim 2: MR Perfusion and Oxygenation

- Oxygenation (BOLD MRI) – multi TE gradient echo sequence = FDA approved sequence

Specific Aim 3: MRI Ferumoxytol DCE perfusion data (not investigational sequences) and localization of immune cells.

DATA AND SAFETY MONITORING

Data and Safety Monitoring Plan

We use the UW ICTR Data Monitoring Committee for the purpose of oversight over this study. We have accounted for the fees for the Data Safety Monitoring. The clinical investigator, [name], the PI, [name] and the co-investigator [name], respectively, are responsible for reporting any adverse responses or events that occur. These are reported as per requirement to UW IRB, and to the Data Monitoring Committee. We take advice from the IRB committee and Data Monitoring Committee for appropriate modifications of our procedures in order to avoid such events.

For subjects receiving the ferumoxytol infusion, the PI and study team will monitor any potential impact on the subject and the fetus. The subject will be closely monitored by triage clinical staff during the infusion of ferumoxytol in the triage unit, including the collection of vital signs. With any signs of reactions, the infusion will be stopped. The study coordinator will report any events of this nature, including adverse events and unanticipated problems, to the PI and the DSMB within one business day.

In the weeks following infusion, the PI will discuss the imaging results with the subject and the clinician providing direct care to the subject. Any adverse events will be documented, entered into the subjects study file and reported to the DSMB. After delivery, pregnancy outcome and any potential impact on the fetus will be documented and reviewed with the PI and subject clinician and DSMB. Development of pre-

eaclampsia and FGR will not be considered, but will be reported, as an adverse event secondary to ferumoxytol infusion.

Data Monitoring Committee (DMC)

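### The protocol fixes in advance that preeclampsia and FGR are not secondary to ferumoxytol, which conflicts with its own rule that a study physician grades each adverse event for relatedness

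*Combined protocol and SAP*

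**What the plan says.** The Data and Safety Monitoring Plan states that the development of preeclampsia and FGR "will not be considered, but will be reported, as an adverse event secondary to ferumoxytol infusion". The same section sends any adverse event to the safety board and has pregnancy outcome reviewed with that board after delivery.

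The Assessment of Safety chapter sets a general procedure. Under Adverse Event (AE), study physicians decide whether each event is expected and whether it is related. Assessment of Attribution repeats this: "The PI or sub-investigator study physicians will assess adverse events to determine the attribution or relatedness to the study procedures and/or intervention". There are five grades, from definitely related to unrelated. Where timing is reasonably consistent with exposure and "there is another cause of the AE that could be equally likely, the PI may categorize the AE as Possible". No exception is made for preeclampsia or FGR.

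The expedited rows under Serious Adverse Event Reporting Requirements apply to events that are serious, suspected or related, and unexpected. The footnote says the IRB wants immediate reports of probably or definitely related serious events, whereas "the FDA requires reporting of these events that are possibly, probably or definitely related". The section on DMC reporting aligns the committee's requirements with the IRB's.

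Adverse Events of Special Interest contains two exemptions. Conditions that obstetricians or pediatricians meet routinely go on the log but not into OnCore, at the investigator's judgement. Events expected in pregnancy and assessed as unrelated to the protocol are neither reported to the DMC nor entered in OnCore.

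On eligibility, a clinical FGR diagnosis is an inclusion criterion, and "Diagnosis of preeclampsia at FGR diagnosis" is an exclusion criterion.

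**The concern.** Relatedness is meant to be judged after an event, on its timing and its competing causes. For two conditions the plan gives the answer beforehand. Preeclampsia is a serious maternal condition that the protocol itself anticipates after the infusion, and hypertension, at 1.0%, is among the reactions it lists for ferumoxytol. That makes relatedness plausible without establishing it, so a blanket negative has no support in the documents.

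At stake is whether a preeclampsia case after infusion gets an individual causality assessment, and whether the DMC can count on seeing it. The study has one group of 20 women and no stopping guideline that covers hypertension or preeclampsia, so little else would bring out a signal.

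**Working it through.** The documents give no figure to reproduce here. The check is a comparison of sections, followed by a short calculation for scale.

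**1. Do the sections conflict?** The attribution section applies to adverse events in general and offers a grade of Possible where another cause is equally likely. Preeclampsia after infusion in a woman with FGR could fit that description, since the underlying placental disease is an obvious competing cause. The Data and Safety Monitoring Plan rules that grade out. A physician cannot follow both.

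**2. Would the events fall after exposure and within collection?** Preeclampsia present at FGR diagnosis is excluded, so any later case is new. Visit 1 places the infusion 1-2 weeks after diagnosis. The text on review and counselling of MRI results, just before Data Collection, Handling, and Record Keeping, says severe FGR or preeclampsia is unlikely until 4-8 weeks after the infusion MRI. Adverse events are collected from consent to 6 weeks after delivery. The protocol therefore expects these events mainly after exposure and inside the collection window.

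**3. What does the fixed answer change in reporting?**

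| Route | Conditions | Effect of the fixed answer |
|---|---|---|
| Expedited, FDA | Serious, unexpected, at least possibly related | Relatedness to ferumoxytol cannot be met |
| Expedited, IRB and DMC | Serious, unexpected, probably or definitely related (footnote) | Relatedness cannot be met, but a grade of Possible would not meet it either |
| Exemption from DMC and OnCore | Expected in pregnancy, and assessed unrelated to the protocol | In effect supplies the unrelated half |

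The last row sits uneasily with the promise that the events will be reported. The exemption's named examples are minor (nausea, back pain and the like), but the list is expressly open. DMC reports are built from OnCore data, so an event kept out of OnCore is also missing from those reports.

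**4. Scale.** The sample size is 20 (Sample Size). No preeclampsia rate is given. Taking 5% to 40% as an assumed range, the expected number of cases is 20 × 0.05 = 1 to 20 × 0.40 = 8.

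Could the overall rate stand in for case-level attribution? The exact (Clopper-Pearson) 95% interval for x cases in 20 runs from the 0.025 quantile of Beta(x, 21 − x) to the 0.975 quantile of Beta(x + 1, 20 − x):

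- 2/20: 1.2% to 31.7%
- 4/20: 5.7% to 43.7%
- 6/20: 11.9% to 54.3%

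Intervals this wide, with no comparison group, could not separate a drug effect from the background rate in women with FGR. Individual assessment, including time from infusion to onset, is what remains.

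**The case against.** The strongest reply is that nothing is lost. The sentence says the conditions will be reported, the same section sends any adverse event to the board, and the standard DMC reports summarise the number and seriousness of events, with no mention of attribution. Individual grading might often give the same answer, because the attribution section allows Unlikely when another cause is more likely.

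Much of this stands. A reader might infer that the sentence removes preeclampsia from IRB, DMC and FDA reporting. The documents do not support that. Expedited reporting also requires the event to be serious and unexpected. The protocol anticipates preeclampsia in these women, so a case may fail the unexpected test whatever its relatedness. Expectedness should not be presumed either, since the Unanticipated Problem definition lets an event count as unexpected if it exceeds the described severity or frequency. A grade of Possible would matter only for the FDA threshold.

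A reader might also size the problem from the listed 1.0% for hypertension. That does not work: the sentence names preeclampsia and FGR, and hypertension without preeclampsia remains open to ordinary grading.

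The FGR half has little effect, because every participant already has that diagnosis; only worsening could be a new event. The statement that "Limited available data with ferumoxytol use in pregnant women are insufficient to inform a drug associated risk of adverse developmental outcomes" concerns developmental outcomes, so it bears on fetal growth and not on maternal preeclampsia.

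What the reply does not remove is the conflict itself, or the tension between the promise to report and the DMC/OnCore exemption. The sentence is also ambiguous: it can even be read as saying the events will be reported as secondary to ferumoxytol.

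**Conclusion.** The concern holds as an internal contradiction about attribution, chiefly for preeclampsia. The plan settles causality for a foreseeable post-infusion event before it happens, while its attribution section requires a physician's judgement each time. The consequence is limited: one necessary condition for expedited reporting is ruled out, decisive at most for FDA reporting of a serious, unexpected case graded possibly related, and the unrelated half of the DMC/OnCore exemption is in effect pre-filled. That any case would actually go unreported is an inference; the text does not say so.

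The number of women affected depends on an unstated preeclampsia rate: 1 to 8 of 20 across the assumed 5% to 40%. The judgement that attribution matters here rests on the small single group and the wide intervals above, not on evidence that ferumoxytol causes preeclampsia. The change is worth making and cheap, and it does not affect the imaging objectives.

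**What to change.** Reconcile the Data and Safety Monitoring Plan, Assessment of Attribution, Adverse Events of Special Interest and the expedited-reporting table. Deleting the sentence alone is not enough: it holds the only explicit promise to report these two conditions, and the exemptions would remain. Replace it with wording such as:

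> Preeclampsia, and worsening of growth restriction beyond the qualifying diagnosis, arising after infusion will be recorded as adverse events; graded individually for severity, expectedness and relatedness under the attribution section; and entered in OnCore and reported to the DMC with infusion-to-onset time, notwithstanding the exemptions for routine or pregnancy-expected events.

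State as well that the FGR that qualified the woman for entry is baseline disease and not an adverse event.

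The cost is one replaced sentence, a cross-reference in the exemptions, and attribution forms for a handful of women. The downside is a few more events to grade, some of which may be rated possibly related. Sample size, study procedures and clinical care are unchanged.
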